## 8.4.2 Early Safety Data Review

### *Sentinel Cohort Safety Evaluation and Safety Parameters*

Two Complete Sentinel ESDRs (CS-ESDR-1 and CS-ESDR-2) will be performed for the Sentinel Cohort. The goal of the CS-ESDRs is to allow the preliminary safety and laboratory parameter assessment of safety data after the first (D01-D09) and the second (D22-D30) vaccine administration to all Initial and all triggered Expanded Cohort participants.

Clinical safety laboratory evaluations will be performed at screening and 8 days after each injection. The first CS-ESDR will be performed for all Sentinel Cohort participants after safety data, including local and systemic AEs, unsolicited AEs, and biological safety laboratory parameters, is obtained from D01-D09 following the first injection. This unblinded review will be performed by the Sponsor during the SMT meetings.

If no safety signals or major tolerability concerns are identified at CS-ESDR-1, the double-blind enrollment of up to 308 participants (vaccine and placebo groups) for the first vaccination of the Full Enrollment Cohort (Cohort 1 allocated to the single-injection schedule and Cohort 2 allocated to the 2-injection schedule) will be initiated. It is to be noted that the first vaccination in the Full Enrollment Cohort may be delayed until after the second vaccination of some of the Sentinel Cohort groups or even postponed until after CS-ESDR-2, if deemed necessary by the SMT.

It is understood that this review is based on preliminary data that have been validated but not subject to database lock. (The usual and ongoing process of monitoring safety signals outside of those specified in the protocol-defined early interim safety analysis will continue unchanged.)

The following safety parameters will be assessed as part of the CS-ESDR:

- Immediate reactions
- Solicited injection site and systemic reactions
- Laboratory abnormalities (including hematology, chemistry, coagulation time, and urinalysis)
- Unsolicited AEs reported as vaccine related by the Investigator
- SAEs and AESIs

Enrollment will be paused during the SMT meeting and the sentinel safety parameters noted will be examined. If any of the below criteria are met for the D01-D09 safety and laboratory data, the

data on the particular alert threshold event will be reviewed by the SMT and a decision will be made as to whether subsequent vaccinations in the study will be allowed to resume or not:

- > 20% of participants experiencing Grade 3 systemic reaction (without concurrent infectious disease) that last for at least 3 days at Grade 3 intensity
- > 20% of participants experiencing Grade 3 solicited injection site pain
- > 20% of participants experiencing Grade 3 unsolicited non serious reactions (reactions not explained by any other possible etiology)
- > 20% of participants with Grade 3 laboratory AE
- > 20% of participants with Grade 2 laboratory AE (reactions not explained by any other possible etiology) and judged by the Investigator to be clinically meaningful
- Any related SAEs or any ICU admission for SARS-CoV-2 infection regardless of relationship to vaccination

A subsequent safety review (CS-ESDR-2) is planned for the Sentinel Cohort participants during which the unblinded SMT will examine the available D22-D30 safety data post-second vaccination including local and systemic AEs, unsolicited AEs, and biological safety laboratory parameters, and all available MAAEs, SAEs, and AESIs for the Sentinel Cohort participants will also be reviewed. If no safety signals or major tolerability concerns are identified during this period in the Sentinel Cohort, then all participants in Cohort 2 will progress to get the second injection (VAC2). If a safety signal or a major tolerability concern is identified at CS-ESDR-2 for the Sentinel Cohort, then Cohort 2 participants for the corresponding dose-level may not receive their second vaccination.

### 8.4.3 Halting Rules for Entire Study

An SMT will review the safety data at regular intervals, to identify any new safety signals or safety concerns during the conduct of the study. The SMT is empowered to recommend a pause in both recruitment and/or further vaccination while it investigates any potential signal or concern. Enrollment will be paused during the review and the data will be examined.

Enrollment and/or further vaccination will be paused if the following alert thresholds are identified:

- Any SAEs assessed as related to the vaccine by the Investigator and the Sponsor
- $\geq 2$  participants experiencing ulceration, abscess or necrosis at the injection site that is considered related to the study vaccine by the Investigator and the Sponsor
- For each vaccine group advanced to the Full Enrollment Cohort (ie, potentially Groups 1 to 3 and Groups 5 to 7, N=44 participants per group [Table 4.3]),  $\geq 4$  participants experiencing any Grade 3 AE (systemic reactions lasting for at least 3 days at Grade 3 intensity, unsolicited AEs and/or clinical laboratory abnormality) in the absence of any other etiology
- Events suggestive of vaccine-associated enhanced disease, including:
  - Any death due to SARS-CoV-2 infection

- > 10% of the study population enrolled at any given time is hospitalized due to SARS-CoV-2 infection
- $\geq 3\%$  of study participants  $\geq 50$  years enrolled at any given time are admitted to the ICU due to SARS-CoV-2 infection
- $\geq 3\%$  of study participants 18 to 49 years enrolled at any given time are admitted to the ICU due to SARS-CoV-2 infection

In addition, ad hoc SMT reviews will occur immediately in the event halting rules are met. Case unblinding may be performed if necessary or if any of the halting rules are met.

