It should be noted that throughout the study, the SMT core members, consisting of Clinical Team Leader (Responsible Medical Officer [RMO]), Study Biostatistician, Pharmacovigilance Science Expert, and Global Safety Officer, will continuously review blinded safety data, except for the safety reviews for the Sentinel Cohort and the planned interim analyses, during which unblinded safety data will be reviewed. The blind will be broken at the group level for the Sponsor at the time of each interim analysis. Further unblinding may be necessary if any of the halting rules are met (see [Section 8.4.3](#)) or if there is any safety concern.

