### 7.1.2 Definitive Contraindications

Participants will permanently discontinue (definitive discontinuation) study intervention for the reasons listed below. These participants must not receive any additional dose of study intervention but should continue to be followed for safety. Additional unscheduled visits may be performed for safety reasons and information will be reported in the source documents.

Should a participant experience 1 of the conditions listed below, the Investigator will discontinue vaccination:

- DCI01: Pregnancy, as indicated by a positive urine test
- DCI02: An anaphylactic or other significant allergic reaction to the previous dose of vaccine
- DCI03: SAE assessed as related to the study vaccine following the previous dose of vaccine, based on Investigator's judgment
- DCI04: A Grade 3 AE, assessed as related to the first study vaccine, that, in the opinion of the Investigator, may place the participant at unreasonable or significant risk of injury or illness following repeat exposure to study vaccine
- DCI05: Symptomatic COVID-19 infection confirmed by NAAT in the period between the first study vaccination (V01) and the day corresponding to the second study vaccination (V03)
- DCI06: Receipt of COVID-19 vaccine (other than the study vaccine) or anti-SARS-CoV-2 monoclonal or polyclonal antibody in the period between the first study vaccination (V01) and the day corresponding to the second study vaccination (V03)

If the participant is enrolled and seeks vaccination of an authorized/approved COVID-19 vaccine outside of the study, he/she will be encouraged to discuss this intention proactively with the study investigator and will be permitted to receive the authorized vaccine at any time. If the participant receives the authorized/approved COVID-19 vaccine, this information would be collected and the participant's data up to the point of receipt of authorized/approved COVID-19 vaccine will be included in the primary analysis for immunogenicity and safety. Participants will be invited to a visit prior to receiving the vaccine and requested to provide a blood sample for immunological assessment. Participants will continue to be followed for the duration of the study as per scheduled visits and procedures except for receipt of the second vaccination as detailed above.

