After the 6-month data (D181 for Cohort 1 and D202 for Sentinel Cohort and Cohort 2) have been collected, a further interim analysis will be performed on immunogenicity, safety, and efficacy endpoints.

A final analysis for all data collected will be conducted once the 12-month safety data have been collected and the final database lock has occurred.

Participant safety will be continuously monitored by the Sponsor's internal safety review committee which includes safety signal detection at any time during the study (see also [Section 8.4.1](#) for Sentinel Cohort dose-escalation, [Section 8.4.2](#) for CS-ESDR details, and [Section 8.4.3](#) for halting rules for the entire study).

The SAP will describe the planned interim analyses and CS-ESDRs in greater detail.

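### The related-SAE halting rule in 8.4.3 needs attribution by both Investigator and Sponsor, so a single non-COVID-19 SAE in the Full Enrollment Cohort can await the Sponsor with no automatic pause

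*Protocol*

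**What the plan says.** Protocol section 8.4.3 lists thresholds at which enrollment, further vaccination or both will be paused. The first is "Any SAEs assessed as related to the vaccine by the Investigator and the Sponsor". The second needs at least two "participants experiencing ulceration, abscess or necrosis at the injection site that is considered related to the study vaccine by the Investigator and the Sponsor". The section closes by saying that "ad hoc SMT reviews will occur immediately in the event halting rules are met".

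Below those thresholds, 8.4.3 has the SMT review safety data at regular intervals and gives it discretion: "The SMT is empowered to recommend a pause in both recruitment and/or further vaccination while it investigates any potential signal or concern". The next sentence says that enrollment is paused while the review takes place. Section 4.1 says that the SMT core members "will continuously review blinded safety data, except for the safety reviews for the Sentinel Cohort and the planned interim analyses". Section 9.5 adds that "Participant safety will be continuously monitored by the Sponsor", through an internal committee. Section 9.6 marks a DMC as not applicable.

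Section 10.3.3 has SAE causality assessed by the Investigator and, separately, by the Sponsor. The Investigator's call must exist before the SAE is first transmitted, and 8.4.4 requires the SAE to reach the Sponsor within 24 hours.

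For the individual participant, 7.1.2 (DCI03) bars further doses after an "SAE assessed as related to the study vaccine following the previous dose of vaccine, based on Investigator" judgment, with no Sponsor agreement needed.

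**The concern.** A halting rule built on single events is meant to act before causality is settled, so that no one else is dosed while the question is open. Read as written, the SAE bullet waits for the second of two opinions. The first opinion arrives with the initial report; nothing in the supplied text says when the second must arrive or what follows if the two differ.

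At stake is the interval between the Investigator's report and Sponsor agreement, or the whole remaining dosing period if the Sponsor disagrees. During that time other participants could be enrolled or given second doses without a mandatory stop. This is a first-in-human study of a new mRNA and a new lipid nanoparticle. Participants aged 50 and over enter at the Full Enrollment stage without a Sentinel group of their own age.

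**Working it through.** No statistical calculation applies and the plan gives no figure to reproduce. The check sets the rules side by side.

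**1. What the SAE bullet does with an Investigator call of related**

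| Sponsor's assessment | Bullet met? | Mandatory pause | Immediate ad hoc review |
|---|---|---|---|
| Related | Yes | Yes | Yes |
| Not related | No | No | No |
| Pending | No | No | No |

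The last column follows the third because 8.4.3 makes the immediate review conditional on a rule being met.

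**2. Timing of the two assessments.** The Investigator's is available at first transmission (10.3.3), which is due within 24 hours (8.4.4). For the Sponsor's, 10.3.3 says only that it is entered in the pharmacovigilance database. No deadline and no tie-break appear in the protocol or SAP. Section 10.3.4 refers to Operating Guidelines, which were not supplied.

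**3. Could another rule catch the same event?**

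- *Injection-site bullet:* needs at least two participants and one specific kind of lesion.
- *Grade 3 bullet:* needs at least 4 participants in one vaccine group of 44. It does not mention the Sponsor, and 8.4.4 counts SAEs among unsolicited AEs, so a Grade 3 SAE with no other etiology can be the event that completes it. A single SAE cannot meet it alone.
- *Enhanced-disease bullets:* the listed criteria concern SARS-CoV-2 infection.
- *Sentinel thresholds (8.4.1 and 8.4.2):* any related SAE requires an SMT decision, with no stated need for both parties to agree. Under 8.4.2 the decision covers vaccinations in the study, with enrollment paused during the meeting. These thresholds use Sentinel data in set windows (D01-D03 and D01-D09), so they do not reach a Full Enrollment event.

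The gap is therefore a single non-COVID-19 SAE, in the Full Enrollment Cohort or in a Sentinel participant outside those windows, that completes no other threshold.

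**4. Who relies on this bullet (Table 4.3, planned numbers)**

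- Vaccine: 6 × 44 = 264. Placebo: 2 × 22 = 44. Total: 264 + 44 = 308. Share on vaccine: 264/308 = 85.7%.
- Aged 50 and over: 6 × 24 = 144 on vaccine, 2 × 12 = 24 on placebo, total 168. Section 4.2 restricts the Sentinel Cohort to ages 18 through 49, so none of the 168 has a Sentinel threshold.

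These figures show how many people the rule serves. They do not estimate how many would be affected by a delay.

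**5. The injection-site bullet.** Section 10.3.3 deems every injection-site AE related and asks for no Investigator opinion. It provides a Sponsor assessment only for SAEs and non-serious AESIs. For a non-serious ulceration that is not an AESI, the bullet refers to a Sponsor assessment the protocol does not otherwise provide.

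**The case against.** The strongest reply is that the study is not left uncovered. The SMT reviews safety data continuously, enrollment stops during its review, it can recommend stopping vaccination too, and DCI03 protects the affected participant on the Investigator's word alone. Ethics committees and regulators also receive SAE reports (8.4.7 and 10.1.1). All of that stands, and it rules out a reading that someone might infer from the bullet: that SMT discretion is the only study-level cover. The Sentinel thresholds, the enrollment pause during review and the Grade 3 bullet each give partial cover. But for the event defined above, none of these forces an immediate review or a halt to second doses. The pause during review is worded for enrollment only.

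A second reply is that requiring two opinions for a mandatory pause is a coherent choice, since the Sentinel thresholds lead only to an SMT decision. That has force. Those thresholds also do not say who judges relatedness, so they are weak evidence that 8.4.3 contradicts the rest of the protocol, and the point does not rest on that contrast.

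Third, the bullet may merely describe who assesses. Then the rule is unclear about disagreement, and the same edit cures it.

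Fourth, a Sponsor deadline may exist in the Operating Guidelines. That is possible; a deadline would shorten the pending interval but would not resolve disagreement.

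Finally, a reader might infer that the injection-site bullet withholds a pause in the same way. The documents do not show that. Given the convention in 10.3.3, its qualifier is redundant or loosely worded.

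**Conclusion.** The point holds within the limits above and is worth correcting as a cheap improvement to a safety rule. It rests on reading the bullet as requiring both attributions, and on the supplied documents containing no Sponsor deadline or disagreement rule.

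Its size is a matter of scope. The bullet is the only single-event related-SAE halting rule for the 308 planned Full Enrollment participants, including all 168 aged 50 and over. The documents say nothing about how often the Sponsor's assessment is late or contrary, so no number of exposed participants or doses can be given. It should not be inferred that delay is common or that the Sponsor would in practice let dosing continue.

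No endpoint, analysis set or estimate changes. The SAP (sections 1 and 5.7) records that vaccination and enrollment were stopped on 27 September 2021, so this is a comment on the rule as planned, to be carried into any protocol that reuses it.

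**What to change.** In the SAE bullet of 8.4.3, replace *and* with *or*, so that attribution by either the Investigator or the Sponsor is enough. Add one sentence: an outstanding Sponsor assessment does not delay the pause, and the ad hoc SMT review decides on resumption.

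In the injection-site bullet, delete the relatedness qualifier, since 10.3.3 already settles it. Changing it to *or* is an acceptable second choice.

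The cost is small. No new data or visits are needed, because the Investigator's causality call is already required before the SAE is first sent. The SMT keeps control of resumption. The downside is an occasional short pause for an SAE later judged unrelated.

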#### 8.4.4 Time Period and Frequency for Collecting AE and SAE Information

##### *Immediate Post-vaccination Observation Period*

Participants will be kept under observation for 30 minutes after each vaccination to ensure their safety. The post-vaccination observation should be documented in the source document.

##### *Reactogenicity*

Solicited injection site reactions will be collected from D01 through D08 after each vaccination.

Solicited systemic reactions will be collected from D01 through D08 after each vaccination.

The solicited injection site reactions and systemic reactions that are pre-listed in the DCs and CRF, together with the intensity scales, are presented in [Appendix 10.3.5.1.1](#).

##### *Unsolicited Adverse Events*

Unsolicited AEs include unsolicited non-serious AEs and SAEs. The intensity grading scale for unsolicited non-serious AEs is presented in [Appendix 10.3.5.1.2](#). Unsolicited non-serious AEs will be collected from D01 to D22 after each vaccination.

SAEs will be collected and assessed throughout the study, ie, before the start of study intervention but after obtaining informed consent until 12 months after the last vaccination (up to D366 for Cohort 1 and up to D387 for Sentinel Cohort and Cohort 2) or the day of study discontinuation for participants who discontinue permanently. However, before the first study intervention administration, only SAEs related to study procedures are to be collected (eg, SAEs related to blood sampling or study procedure performed during a screening visit).

Medical occurrences that begin before the start of study intervention but after obtaining informed consent will be recorded on the AE section of the CRF.

All SAEs will be recorded and reported to the Sponsor or designee immediately and under no circumstance should this exceed 24 hours, as indicated in [Appendix 10.3](#). The Investigator will submit any updated SAE data to the Sponsor within 24 hours of it being available.

Investigators are not obligated to actively seek AE or SAE after conclusion of the study participation. However, if the Investigator learns of any SAE, including a death, at any time after a participant has been discharged from the study, and he/she considers the event to be reasonably related to the study intervention or study participation, the Investigator must promptly notify the Sponsor.

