‡‡‡‡‡ All participants will be scheduled to attend V08 for blood sampling and 12-Month (post-VAC2) Safety Follow-up. However, if any participants discontinue the study early, they are still to be followed for safety and are to be contacted with a Safety Follow-up call to identify the occurrence of any SAEs and AESIs that had not yet been reported. If discontinuation occurs at a scheduled visit, the participant will be provided a Memory Aid instead of a DC for SAE follow-up (including AESIs) until the Safety Follow-up call. If a participant discontinues between visits (with no Memory Aid provided yet), the participant will use the last DC received to collect information for the Safety Follow-up call.

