## 7.2 Participant Discontinuation/Withdrawal from the Study

- A participant may withdraw from the study at any time at his/her own request or may be withdrawn at any time at the discretion of the Investigator for safety, behavioral, compliance, or administrative reasons. This is expected to be uncommon.

- The reason for withdrawal should be clearly documented in the source documents and in the CRF: AE, Lost to Follow-up, Protocol Deviation, or Withdrawal by Participant.
- The participant will be permanently discontinued both from the study intervention and from the study at that time.
- If the participant withdraws consent for disclosure of future information, the Sponsor may retain and continue to use any data collected before such a withdrawal of consent.
- If a participant withdraws consent, he/she may request destruction of any samples taken and not tested, and the Investigator must document this in the site study records.
- Withdrawn participants will not be replaced.

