### ***Follow-up of Discontinuations***

For participants who have prematurely terminated the study, the site should attempt to contact them and complete all scheduled safety follow-ups, except if they specified that they do not want to be contacted again and it is documented in the source document.

For participants where the reason for early termination is lost to follow-up, the site will not attempt to obtain further safety information. See [Section 7.3](#) for definition of “lost to follow-up”.

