## **8.4.5 Method of Detecting AEs and SAEs**

Individual DCs, specifically designed for this study by the Sponsor and provided to the study sites, will be given to study participants for the recording of daily safety information. These DCs will include pre-listed terms and intensity scales as well as areas for free text to capture additional safety information or other relevant details. Participants will also be provided with rulers for measuring the size of injection site reactions, and with standard digital thermometers for measuring daily temperatures. To ensure consistency of reporting, the study sites will instruct participants on how to correctly use these tools.

At specified intervals, the Investigator or an authorized designee will interview the participants to collect the information recorded in the DC and will attempt to clarify anything that is incomplete or unclear. All clinical study information gathered by the study site will be reported electronically by the Investigator or authorized designee using a web-based CRF. Any information that was not documented in the DC will first be captured in the source document and then reported electronically.

The 12-month (post-last injection) follow-up will be done by interviewing participants during a visit (or over the telephone for participants who discontinue early from the study) using a questionnaire to capture SAEs and AESIs, if applicable.

The method of recording, evaluating, and assessing causal relationship of AE and SAE and the procedures for completing and transmitting SAE reports are provided in [Appendix 10.3](#).

Care will be taken not to introduce bias when detecting AEs and/or SAEs. Open-ended and non-leading verbal questioning of the participant is the preferred method to inquire about AE occurrences.

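### Protocol 8.4.4 stops SAE collection on the day a participant leaves the study, while the schedules, 7.2 and 8.4.5 require safety follow-up of the same people; the sections need reconciling

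*Protocol*

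**What the plan says.** Protocol 8.4.4, under Unsolicited Adverse Events, sets the SAE window. It runs to 12 months after the last vaccination (D366 in Cohort 1, D387 in the Sentinel Cohort and Cohort 2) "or the day of study discontinuation for participants who discontinue permanently".

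Section 7.2 applies that status to everyone who withdraws: "The participant will be permanently discontinued both from the study intervention and from the study at that time".

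Other places give a different rule for the same people:

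- **Table 1.5 footnote (Cohort 2):** "if any participants discontinue the study early, they are still to be followed for safety and are to be contacted with a Safety Follow-up call". Table 1.3 carries the same rule, and Table 1.4 calls it a 12-month call. The purpose is to find SAEs and AESIs not yet reported, with a Memory Aid or the last Diary Card used until then. Each schedule also has a 12-month follow-up record reserved for those who discontinued early.
- **7.2, Follow-up of Discontinuations:** "the site should attempt to contact them and complete all scheduled safety follow-ups", with two exceptions. One is participants who refuse ("except if they specified that they do not want to be contacted again"). The other is those lost to follow-up: "For participants where the reason for early termination is lost to follow-up, the site will not attempt to obtain further safety information".
- **8.4.5:** the 12-month interview for SAEs and AESIs is held at a visit, "or over the telephone for participants who discontinue early from the study".

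SAEs throughout the study are a primary safety endpoint (Table 3.1), and the primary safety objective runs to 12 months post-last dose.

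**The concern.** Section 8.4.4 is where a site would look for the SAE collection period, and its stop is not limited to participants who refuse contact or cannot be reached. Read alone, it lets active SAE ascertainment end for anyone who leaves the study, including people who would answer a call. Adverse event is one of the withdrawal reasons listed in 7.2, so leaving can be connected with safety.

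Early leavers stay in the Safety Analysis Set, which needs only one injection, and SAE results are percentages of participants. An SAE missed after leaving can remove a case from the numerator while the denominator stays the same. Any error therefore lowers the observed percentage, and two sites reading different sections could record different data for the same kind of participant.

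**Working it through.** **1. Do the sections cover the same people?**

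| Early leaver | 8.4.4 | Schedules, 7.2 follow-up rule, 8.4.5 |
|---|---|---|
| Can be contacted | SAE collection ends on the day of leaving | Safety follow-up continues, with a call for SAEs and AESIs |
| Refuses contact | Ends on the day of leaving | 7.2 ends contact |
| Lost to follow-up | Ends on the day of leaving | 7.2 ends attempts |
| Stops vaccination only (7.1.2) | Not a study discontinuation | Continues to be followed for safety |

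The conflict is confined to the first row. The word *permanently* in 8.4.4 does not limit the stop to the two middle rows, because 7.2 uses the same term for every withdrawal.

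**2. The plan's own durations.** The last contact is 365 days after the last injection. In Cohort 1, D01 + 365 = D366, which is 365 days. In the Sentinel Cohort and Cohort 2, D01 + 21 + 365 = D387, which is 386 days. Both match the stated durations.

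**3. Active SAE follow-up lost by one early leaver under 8.4.4.** Share lost = (end day − day of leaving) / planned duration. D43 is chosen because it is the plan's key follow-up timepoint.

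| Planned end | Leaves at | Days lost | Share |
|---|---|---|---|
| Cohort 1, D366 | D22 | 366 − 22 = 344 of 365 | 94.2% |
| Cohort 1, D366 | D43 | 366 − 43 = 323 of 365 | 88.5% |
| Cohort 1, D366 | D181 | 366 − 181 = 185 of 365 | 50.7% |
| Cohort 2, D387 | D22 | 387 − 22 = 365 of 386 | 94.6% |
| Cohort 2, D387 | D43 | 387 − 43 = 344 of 386 | 89.1% |
| Cohort 2, D387 | D202 | 387 − 202 = 185 of 386 | 47.9% |

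More than half is lost by anyone leaving before about D183 in Cohort 1 (1 + 365/2 = 183.5) or D194 in Cohort 2 (1 + 386/2 = 194).

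**4. With the 6-month end in the SAP** (introduction and 5.7), taking it as D181 or D202:

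- Cohort 1, leaving at D43: (181 − 43)/180 = 138/180 = 76.7%.
- Cohort 2, leaving at D43: (202 − 43)/201 = 159/201 = 79.1%.

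**5. Across a group.** The documents give no dropout rate. Purely as an assumption, suppose 2% to 20% of a Cohort 1 group leave at D43, all can be contacted, and every site applies 8.4.4. The share of planned person-time lost is then 0.02 × 323/365 = 1.8% to 0.20 × 323/365 = 17.7%. This is person-time, not a change in the SAE percentage, which also depends on event rates after leaving.

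**6. If the sections agreed** on the 7.2 rule, a contactable early leaver would lose nothing by rule.

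**The case against.** The strongest reply is that the intent is clear and this is one stray clause. Section 8 makes adherence to the schedules of activities essential and allows no waivers. All three schedules require the call, and 7.2 and 8.4.5 repeat the duty. A reader might infer that a site could skip the call and still be compliant; section 8 does not support that. What stands is that 8.4.4 states a contrary rule with no cross-reference, so a site could apply it in error.

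A reader might also infer that nothing is observed after leaving. That is too strong. Section 8.4.4 itself requires prompt notification of any SAE the investigator learns of later and considers reasonably related. Section 8.4.6 follows AEs that are related, or that caused discontinuation, until they resolve, stabilise or become chronic. What would be lost is active searching: unrelated SAEs, and related ones that nobody reports. The endpoint counts any SAE, so this is not a full answer.

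A third inference, that AESIs have a longer window than SAEs in the same person, is weak. AESIs are collected at any time during the study, which could equally end at withdrawal, and the schedules collect them as SAEs through the same call.

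Finally, the SAP does not adopt the cut-off. It counts SAEs over the entire study and, for participants without an outside COVID-19 vaccine, uses safety data to the last phone contact. That settles which collected data are analysed, but it cannot restore events that were never collected.

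**Conclusion.** The contradiction is real, and 8.4.4 is wrong as written for early leavers who can still be contacted. For one such person leaving at D43, the rule gives up as much as 89% (Cohort 2) or 88% (Cohort 1) of planned active SAE follow-up, or 79% (Cohort 2) with the 6-month end. These figures assume that the site applies 8.4.4 alone and that the participant would have answered a call.

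They should not be read as a loss of that size from the primary endpoint, nor as showing that the SAE percentages are biased. The documents give no dropout rate, 7.2 expects withdrawal to be uncommon, and nothing shows that any site followed 8.4.4 over the schedules. The supported conclusion is that the percentage could be understated, by an amount that cannot be calculated from the documents, and that ascertainment could differ by site.

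**What to change.** Reconcile the sections. Replace the clause in 8.4.4 with a cross-reference to Follow-up of Discontinuations in 7.2. SAE collection for early leavers would then continue to the end of planned safety follow-up: 12 months, or 6 months after the early end recorded in the SAP. The exceptions would be the two already in 7.2, refusal of contact and loss to follow-up.

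In the CSR, report the last safety contact date for early leavers and the number without completed safety follow-up. Enrollment and vaccination have ended, so this is the more useful step now: it lets a reader judge how complete the SAE percentages are.

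The cost is wording in one section and a short addition to the CSR. The call, the Memory Aid and the CRF record for early leavers are already in the schedules.
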